9.4.3 ANALYSIS OF THE SECONDARY ENDPOINT(S)

Our secondary hypotheses are:

- (a) We hypothesize that there will be a significantly greater association between the change in depression symptoms (as measured by the MADRS-S) and the change in resting-state functional connectivity between the subgenual anterior cingulate cortex and the default mode network from baseline to after intervention day 5 for participants receiving active as compared to sham aiTBS.
- (b) We hypothesize that there will be a significantly greater association between acute mood state (as measured by the IMS-12) and the change in resting-state functional connectivity between the subgenual anterior cingulate cortex and the default mode network from baseline to after intervention day 5 for participants receiving active as compared to sham aiTBS.

We will use fMRI to measure resting-state FC between sgACC & DMN. Participants will be treated for 5 consecutive days with 10 sessions per day of active or sham aiTBS. Participants have a baseline MRI scan prior to each day of aiTBS intervention as well as the day following the completion of intervention. After standard preprocessing of fMRI data, we will calculate FC as the correlation of the activity pattern across time between the sgACC and DMN regions of interest. All correlation coefficients will then be transformed into Fisher's Z score for further analysis.

MADRS-S will be collected at baseline, the end of each intervention day, and the day following intervention. IMS-12 will be collected at baseline, on the morning of each intervention day, and the day following intervention.

Normality in change in both assessments and change in FC from baseline to post-intervention will be assessed via Shapiro-Wilk. Appropriate correlational analysis (Pearson or Spearman) will be used to quantify the association between change in FC and change in each assessment for each treatment group. Correlation coefficients will be compared statistically by performing Fisher's R-to-Z transformation and the difference between the two Z-scores will be tested for statistical significance using a two-tailed Z-test with an alpha level of 0.05 ($p < 0.05$). The null hypothesis, i.e. no difference in the association between change in FC and change in each assessment between groups, will be rejected if the Z-test has a p-value < 0.05 .

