9.2 SAMPLE SIZE DETERMINATION

Sample size justification (power analysis):

Key Hypothesis of the study: A significant reduction in functional connectivity between sgACC and DMN. We hypothesize that the reduction in functional connectivity between the subgenual cingulate cortex and the default mode network from baseline to after intervention day 5 will be significantly greater for participants receiving active compared to sham aiTBS. Several past studies have found no significant changes in functional connectivity with sham rTMS targeted to DLPFC^{136,212}. Using preliminary data from our open-label study of aiTBS for treatment of severe depression, there was an effect size of 1-1.47 (depending on DMN node) for change in connectivity between sgACC and DMN¹⁵⁰. One potential approach for determining the power calculation would be that considering we will have 10 unique comparisons with each day's data be compared to every other day over 5 days, and that we will be comparing across 4 DMN nodes and 2 sgACC nodes, our target alpha needs to be $0.05/(10*4*2) = 0.000625$. Thus, for an effect size of 1, alpha of 0.000625, and a power of 0.80, and powering for an independent-measures t-test, 40 participants will be required for each arm. Regarding our secondary mechanistic endpoints, we have previously found a significant correlation between change in FC between sgACC and DMN in participants receiving open-lab aiTBS, Pearson $r = 0.51$. For a point biserial model, a two-tailed 2 test, and a power target of 0.80, 25 participants will be required for each group.

Our recruitment goals are based on our primary mechanistic endpoint. Considering a ~25% attrition rate (combined participants lost to followup and unusable or missing scans), **we plan to recruit 50 participants in each arm**, as this is larger than the 18 per arm that is required to power for a significant reduction in IMS-12, and large enough to provide sufficient power for our secondary mechanistic endpoints. Given that there are ~1,000 new depressed patients at Stanford per year, >75% are TMS-naïve, there are many more than 100 patients per year that meet inclusion criteria.

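### Section 9.4.3 gives no standard error for Spearman and does not require the same coefficient in both arms; under the usual Fisher variance the type I error is near 5% for near-normal data but about 8–10% with heavy tails

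*Combined protocol and SAP*

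**What the plan says.** Section 9.4.3 specifies one procedure for both secondary hypotheses (MADRS-S and IMS-12).

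- **Pre-test.** The changes in the two assessments are checked for normality, and "change in FC from baseline to post-intervention will be assessed via Shapiro-Wilk". No cut-off is given. The section does not say whether the check is pooled or by arm, or what follows if only one variable or one arm fails.
- **Coefficient.** The section says "Appropriate correlational analysis (Pearson or Spearman) will be used to quantify the association" and applies this to "change in FC and change in each assessment for each treatment group".
- **Comparison.** "Correlation coefficients will be compared statistically by performing Fisher's R-to-Z transformation". After that, "the difference between the two Z-scores will be tested for statistical significance", and the test is specified as one made "using a two-tailed Z-test with an alpha level of 0.05".

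No standard error is written for the Z-test. Nothing in Sections 9.2 or 9.4.1 supplies one, and nothing says that the two arms must use the same coefficient.

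**The concern.** Fisher's transformation gives a variance of 1/(n−3) for a Pearson correlation under bivariate normality. For a Spearman correlation the variance is larger once the true correlation is not zero. Section 9.4.3 turns to Spearman when normality fails, and it offers no other variance when it does. An analyst filling the gap in the usual way would then use too small a standard error in the situation that the pre-test is meant to handle.

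The second gap is the missing same-coefficient rule. If normality fails in one arm only, the text allows a Pearson z in one arm to be subtracted from a Spearman z in the other. The two coefficients estimate different quantities, so that difference has no clear meaning.

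Different shapes by arm are conceivable. MADRS-S is bounded at 0 to 27 (Section 8.2). In the open-label MDD data in Section 2.2, post-treatment MADRS averaged 4.833 with SD 5.813 and range 0–19, which suggests a floor after active treatment.

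At stake is the claim that connectivity change tracks symptom change more closely under active than under sham stimulation. This is the only test specified for it.

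**Working it through.** **Inputs from the documents.** Alpha is 0.05, two-sided (9.4.3). There are 50 per arm with about 25% attrition (9.2), so 50 × 0.75 = 37.5, or about 38 evaluable per arm. The planning correlation is 0.51 (9.2).

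**Inputs assumed.** The documents give neither the correlation shared by the arms under the null nor the shape of the change scores. Shared correlations from 0 to 0.85 were tried with normal, skewed (exponentiated-normal), rounded and bounded, and heavy-tailed (bivariate t with 4 or 5 df) data. A Shapiro-Wilk cut-off of 0.05 was assumed, with failure of either variable leading to Spearman.

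**1. The plan's own figure.** Section 9.2 says that with "a power target of 0.80, 25 participants will be required for each group". A test of one correlation against zero has noncentrality √(r²/(1−r²))·√N. With r = 0.51 this is √(0.2601/0.7399) × √25 = 0.593 × 5 = 2.96. Power is 0.793 at N = 24 and 0.810 at N = 25, so 25 reproduces. It is the size for one correlation against zero and says nothing about the error rate of the difference test.

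**2. The test under the natural reading.** z = (atanh r₁ − atanh r₂)/√(2/(n−3)). At n = 38 the denominator is √(2/35) = 0.239.

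**3. Size of the Spearman shortfall.** An approximate Spearman variance is (1 + r²/2)/(n−3). At r = 0.51 the factor is 1 + 0.2601/2 = 1.130, so the standard error is understated by a factor of √1.130 = 1.063. The effective critical value is 1.96/1.063 = 1.844, which has a two-sided tail of about 6.5%. Simulation gives a little less, because that formula is slightly too large (used as the variance, it gives 4.4% at 0.51).

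Spearman in both arms with the 1/(n−3) variance, bivariate normal data, 40,000 replicates:

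| Shared ρ | n = 37 | n = 50 |
|---|---|---|
| 0 | 5.0% | 5.1% |
| 0.3 | 5.2% | 5.4% |
| 0.51 | 5.9% | 5.7% |
| 0.7 | 6.3% | 6.5% |
| 0.85 | 7.6% | 7.6% |

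Rounded and bounded scores behave the same way (5.8% at ρ = 0.51, n = 37), so the bounded scale is not itself the problem.

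**4. The whole rule, including the pre-test.** 38 per arm, equal association in both arms, shared ρ up to 0.7:

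| Data | Rule as read | Arms get different coefficients | Pearson throughout, same Z-test |
|---|---|---|---|
| Normal | 4.6–5.4% | 16–18% of trials | about 5% |
| Skewed in both arms | 4.8–6.6% | 0–0.3% | up to 26% |
| Heavy tails (t, 5 df) | 7.8–10.2% | about 50% | about 14% |

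A separate heavy-tailed run of 5,000 trials gave 8.2%, 8.5%, 9.0% and 10.5% at ρ = 0, 0.3, 0.51 and 0.7 with choice by arm, and 7.4–10.3% with a common coefficient. Most of the excess therefore remains when both arms use the same coefficient.

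**5. One arm skewed, the other normal (n = 40).** The arms got different coefficients in about 90% of trials, yet the error was 4.8–5.0% for ρ from 0 to 0.51.

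**6. Different quantities.** With t (4 df) data at ρ = 0.51 and n = 37, the mean Pearson is 0.498 and the mean Spearman 0.468. On the z scale the gap is 0.547 − 0.508 = 0.039, about 0.16 of the standard error √(2/34) = 0.243. The offset is small here, but it would be counted as a treatment difference.

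**7. Remedies under heavy tails.** Spearman with the (1 + r²/2)/(n−3) variance still rejects in 5.4–6.2% (t, 5 df). Spearman in both arms with a bootstrap standard error gave 3.1–5.3% across all scenarios.

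**The case against.** **The plan states neither disputed step.** It does not say that 1/(n−3) will be used for Spearman, and it does not say that the coefficient may differ by arm. Computing an association in each treatment group is needed for any comparison of arms, and one coefficient per outcome is at least as natural a reading. This stands. The defect is that the text leaves both steps to the analyst.

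**A reader might infer that the false-positive rate exceeds 5% in general.** The working does not support that. With near-normal data the rule holds its level to within simulation error (about 0.3 point). Spearman throughout at the protocol's own 0.51 is less than 1 point over. Material inflation needs heavy tails or a very strong shared correlation, and the documents give evidence of neither.

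**A reader might also infer that mixing coefficients pushes the error far above 10% with skewed data.** That happens only if Pearson is forced on one skewed arm and Spearman on the other. The rule would almost never do this, because the pre-test sends both skewed arms to Spearman. With only one arm skewed, mixing is common but the error stays near 5%.

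**Switching to Spearman helps.** Where the rule inflates, Pearson with the same Z-test is worse. This stands too: the fault lies in the variance and the loose selection rule, and it would be wrong to read the point as a case for Pearson.

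**The endpoint is secondary.** The primary analysis in Section 9.4.2 is unaffected.

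**Conclusion.** The point holds in a limited form. Section 9.4.3 sends either coefficient through one Z-test, with no Spearman standard error and no same-coefficient rule. If the usual 1/(n−3) variance is used, the type I error at about 38 per arm is close to 5% for near-normal data. It reaches about 6.6% with skewed data and a strong shared correlation, and about 8–10% with heavy tails. With heavy tails and choice by arm, about half of trials would compare a Pearson with a Spearman coefficient, which is a problem of interpretation whatever its effect on the error rate.

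These figures rest on an assumed standard error, an assumed 0.05 Shapiro-Wilk cut-off, assumed distributions and an assumed non-zero correlation common to both arms where one is used. The heavy-tailed case is a bivariate t, in which extreme values tend to occur together in both variables. The documents do not show that the trial's change scores look like this. The change is still worth making, because a better method is available at almost no cost.

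**What to change.** Amend Section 9.4.3 before unblinding:

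- Remove the Shapiro-Wilk step as a selector of the coefficient.
- Prespecify Spearman, with mid-ranks for ties, in both arms and for both MADRS-S and IMS-12.
- Test the difference between the two Fisher-z values with a bootstrap standard error, resampling participants within arm. State the number of resamples and the seed.

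Do not fix Pearson and keep the present Z-test: that rejects in about 14% with heavy tails and up to 26% with skew. Do not rely on the (1 + r²/2)/(n−3) variance alone if tails may be heavy.

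**Cost.** A paragraph of text and a few lines of code, with no change to data collection. The test becomes slightly more conservative. As a guide, take 0.51 in the active arm against an assumed 0 in sham, at 38 per arm. Power with the 1/(n−3) variance is Φ(0.563/0.239 − 1.96) = 0.65. With the larger approximate Spearman variance the standard error is √(2.130/35) = 0.247 and power is 0.63, a loss of about 3 points before rounding (0.653 to 0.626). This ignores the slightly lower expected value of Spearman itself.

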This study is **innovative** technologically in its approach to rapidly modulate the neural circuitry underlying depression and measure the functional connectivity changes resulting from that modulation using precision medicine. This efficacy and rapidity is achieved via several technological innovations over conventional rTMS: 1) The number of pulses given per day (18,000) is higher than any other known application, and this may address potential under dosing of rTMS in treatment of depression^{84,90}. 2) iTBS is more efficient than rTMS at a pulse ratio of 1:5 with 1 pulse of iTBS equivalent to 5 10Hz rTMS pulses and at a time ratio of 1:12.3 with every 1 min of iTBS being equivalent to 12.3 min of 10Hz rTMS⁸¹. 3) We space iTBS sessions at 60-min intervals, which may be optimal for producing long-term potentiation via iTBS as shown by studies of synaptic potentiation¹⁵³. Notably, theta-burst trains that are spaced by 60 min result in over twice the magnitude of potentiation as trains spaced by 30 min, and trains spaced by 60 min induce the same magnitude of synaptic potentiation as those spaced by 90 min¹⁵³. 4) We account for the significant variability in head anatomy¹⁵⁴. 5) We employ an automated personalized targeting approach based a hierarchical clustering algorithm to identify functional subregions of the L-DLPFC & sgACC. A separate decision-making algorithm then evaluates the size, shape, and the functional connectivity relationships between each L-DLPFC subregion and each sgACC subregion in order to identify the optimal L-DLPFC target with an existing anti-correlation functional connectivity relationship with the sgACC. The advantages of aiTBS also include more rapid delivery of treatment, more rapid improvement in symptoms, and fewer needed visits; thus, likely enhancing retention and treatment completion. aiTBS provides a new opportunity to begin investigating the network alterations underlying MDD remission. Fc changes that occur with aiTBS may reflect generalized network-level changes associated with remission from depression. Given that we found that fc significantly decreases between several of these regions following aiTBS-induced remission from MDD, the magnitude of fc change often correlating with symptom improvement, and the pre-treatment connectivity between several regions to be predictive of the magnitude of this improvement, this study will allow for an opportunity to study the nature of the trajectory of the fc changes in relation to clinical changes^{5,86}.

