3 OBJECTIVES AND ENDPOINTS

OBJECTIVES	ENDPOINTS	JUSTIFICATION FOR ENDPOINTS
Primary		
To establish a resting state functional connectivity (RS FC) dose-response curve of active versus sham aiTBS.	Change in RS FC between the sgACC and DMN over 5-days of active aiTBS as compared to sham aiTBS. RS FC will be measured on the morning of each intervention day and the day following intervention.	We hypothesize that participants (n=50) receiving active aiTBS applied to DLPFC-sgACC will demonstrate a significant attenuation of RS FC between sgACC and DMN compared to sham (n=50) after each day of stimulation and these effects will accumulate linearly over the course of the 5 days of aiTBS. The central, consistent change in neurocircuitry observed in depression is hyperconnectivity between the SCC and DMN ⁴³ and our preliminary data involving RS FC changes from aiTBS demonstrates highly significant changes ¹⁹⁴ .
Secondary		

(a) To determine the relationship between active versus sham aiTBS-induced clinical improvement (as measured by reduction of the MADRS-S) and changes in RS FC between the sgACC and DMN.
 
(b) To determine the relationship between acute mood state (as measured by the IMS-12) and changes in RS FC between the sgACC and DMN in those receiving active versus sham aiTBS.
	
(a) Relationship between clinical improvement (measured by the MADRS-S) and RS FC between the sgACC and DMN.
 
MADRS-S will be collected at baseline, the end of each intervention day, the day following intervention, and 1-month after intervention. RS FC will be measured on the morning of each intervention day and the day following intervention.
 
(b) Relationship between acute mood state (measured by the IMS-12) and RS FC between the sgACC and DMN.
 
IMS-12 will be collected at baseline, on the morning of each intervention day, and the day following intervention. RS FC will
	Our mechanistic hypothesis is that active versus sham aiTBS-induced improvement in mood will be linear, related to session number (accumulated pulse dose), and will be associated with (accumulated) decrease in sgACC- DMN resting state functional connectivity, as compared to sham.

	be measured on the morning of each intervention day and the day following intervention.	
Exploratory		

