- ***Radiographic or other imaging assessments:*** All participants will undergo magnetic resonance imaging (MRI) evaluations at: baseline (morning prior to first TMS session) and each subsequent morning throughout the five-day TMS course (visits 3-8). MRI acquisitions will include T1-weighted structural and resting state functional magnetic resonance imaging sequences. Participants will be instructed to keep their eyes open and concentrate on a fixation cross for the duration of the resting state fMRI scan and to lie as still as possible. The fixation cross will be presented via a projector system and visualized through a mirror on the head coil. Subjects will confirm verbally during setup that the fixation cross is centered within their visual field, which can be adjusted via the head coil mirror angle. The image quality of the baseline scan will be evaluated for quality assurance, it is important that these are assessed, as they are the bases for our personalized targeting generation, as well as subsequent determination of a dose-response curve. We anticipate little to no group differences in functional connectivity between the active and sham groups at the time of baseline acquisition due to random allocation; however, this will be confirmed statistically post study completion. Following the establishment of fMRI baseline, we hypothesize that we will observe functional connectivity changes that are linearly correlated with the effects of the 5-day active TMS intervention.
- ***Administration of questionnaires or other instruments:*** The clinical active versus sham aiTBS-induced effect will be tested using either the standard (72-hour) version or a 24-hour version of the MADRS-S depending on time point (clinical improvement) and IMS-12 (acute mood state). **On the morning after the 5th day of stimulation (visit 8), participants will receive the IMS-12, MADRS-S and YMRS at the same visit as their MRI scan.**
- ***Additional optional blood draw study:***

An additional optional procedure consisting of three blood draws will be available to participants in this trial. These blood draws will occur on the In-person Screening 2/Baseline (Visit 2), the next day (Visit 8), and one-month follow up visit (Visit 9).

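### Both secondary tests use only the first and last visit, so no planned analysis relates the daily sgACC-DMN trajectory to mood

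*Combined protocol and SAP*

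**What the plan says.** **Data collected.** Section 8.1 schedules MRI at "baseline (morning prior to first TMS session) and each subsequent morning throughout the five-day TMS course (visits 3-8"), which is six scans. Section 3 states that "IMS-12 will be collected at baseline, on the morning of each intervention day, and the day following intervention", so IMS-12 shares those six mornings. Section 9.4.3 states that "MADRS-S will be collected at baseline, the end of each intervention day, and the day following intervention". The version of that scale is "either the standard (72-hour) version or a 24-hour version of the MADRS-S depending on time point" (8.1). The Schedule of Activities puts the standard version at screening, baseline and Visit 3, and the 24-hour version at Visits 4 to 8.

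**Data analysed.** In 9.4.3, "Normality in change in both assessments and change in FC from baseline to post-intervention will be assessed via Shapiro-Wilk". A correlation then "will be used to quantify the association between change in FC and change in each assessment for each treatment group", and the two coefficients are compared by a two-tailed Z-test at 0.05. Both hypotheses concern change "from baseline to after intervention day 5 for participants receiving active as compared to sham aiTBS". No repeated-measures term appears.

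**Stated purpose.** Section 2.1 presents the trial as "an opportunity to study the nature of the trajectory of the fc changes in relation to clinical changes". The synopsis and section 3 hypothesise that mood improves linearly with session number and that this improvement goes with the accumulating fall in sgACC-DMN connectivity.

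**The concern.** A first-to-last difference cannot show whether improvement is linear over sessions, whether mood follows FC within a patient, or which moves first. It compares people with one another and rests on two single scans.

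The protocol's own background suggests that the omitted visits could matter:

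- Section 2.2 reports a mean of 2.96 (SD 1.48) days to remission in the open-label series, with mean MADRS down to 4.65 after five days. If that recurs, much of the mood change in the active arm falls within Visits 4 to 7.
- Section 2.1 reports that the smallest reductions in midline FC went with the best outcomes, and cites ECT data in which an early FC decrease predicted a later increase. A path that falls and then rises cannot be seen in a two-point difference.
- Section 9.2 expects about 25% loss, including unusable or missing scans. A participant without a usable Visit 8 scan has no change score and leaves both secondary tests, whatever the other mornings show.

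**Working it through.** **1. Is the daily series related to mood anywhere in the plan?**

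- 9.4.2 (primary): mixed model over all scans; FC is the outcome and no mood variable enters.
- 9.4.3 (secondary): two time points only.
- 9.4.9 (exploratory): network segregation is compared between baseline and post-intervention and regressed against mood. Excitation/inhibition balance is taken before and after. The topological analysis follows dose over the course but names no mood outcome.
- Section 3 lists daily mood measures for the exploratory whole-brain objectives, but 9.4.9 gives no repeated-measures FC-mood model. The general mixed-model sentence in 9.4.1 does not fill the gap, because 9.4.3 names a specific correlation method.

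So the daily sgACC-DMN series is not paired with mood in any planned analysis.

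**2. Data unused in the secondary tests.** Six visits less two used leaves 4/6 = 67%. At 40 evaluable per arm: 40 × 6 = 240 FC-IMS-12 pairs, 40 × 2 = 80 used, 160 unused. The count is exact for IMS-12 only, since MADRS-S is taken in the evening on treatment days.

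**3. The plan's own secondary figure.** Section 9.2 gives 25 per group for r = 0.51, two-tailed, power 0.80. One correlation against zero, with noncentrality √(N·r²/(1−r²)) = √(25 × 0.2601/0.7399) = 2.96 on 23 df, gives power 0.810, so 25 reproduces. The test in 9.4.3 is a different one. With atanh(0.51) = 0.563, sham r = 0 (assumed) and SE = √(2/(n−3)):

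- n = 25: SE 0.302, power 0.46
- n = 40: SE 0.232, 0.563/0.232 = 2.42, power Φ(2.42 − 1.96) = 0.68

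The 0.68 is the benchmark below. The mismatch in the 25 is a separate matter.

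**4. What six visits would add.** The documents give no within-person covariance of FC and mood, so the results below rest on assumed structures. Simulation: six visits, 40 per arm, association in active and none in sham. The within-person model removes person and arm-by-visit means and uses participant-clustered SEs.

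| Assumed structure | Planned test | Six-visit analysis |
|---|---|---|
| Person slopes coupled only (change r = 0.51): within-person model | 68–71% | 55–68% |
| Same, per-person six-visit slopes correlated, independent noise, 55–80% of change variance true | 67–69% | 75–83% |
| Same, 90% true | 69% | 72% |
| Same, AR(1) 0.5 noise | about 68% | about 68% |
| Day-to-day coupling r = 0.30: within-person model | 27–28% | 76–85% |
| Day-to-day coupling r = 0.51: within-person model | 69–71% | above 99% |

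The first row falls because, when only slopes are coupled, scan noise at every visit dilutes the within-person regression. Per-person slopes recover that signal. They gain nothing under purely day-to-day coupling, because a slope, like a change score, is one contrast per person.

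**5. Type I error.** With day-level data and no coupling, the clustered-SE model gave about 4.5% to 5.5%. With only a participant intercept and model-based SEs, and person slopes that vary but are uncoupled, the error was about 7% to 26%, rising with the share of true change.

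**The case against.** The strongest reply is that 9.4.3 tests what 9.1 states: change from baseline to after day 5, compared between arms. The r = 0.51 in 9.2 is also described as a correlation with change in FC. A within-person daily model targets a different quantity, for which the documents give no preliminary value, and its large power gains come from building day-to-day coupling into the simulation. All of this stands, and it is why the planned test should remain.

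A reader might infer that the daily scans contribute nothing to the mechanistic endpoints. That is not so: 9.1 labels the FC endpoint the primary mechanistic endpoint, and its mixed model in 9.4.2 takes time as the repeated measure. Only the secondary tests leave out Visits 4 to 7.

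Two technical objections also hold. Arm-by-visit terms remove each arm's average trajectory, so the FC-by-arm term then tests deviations around it and not the linear session hypothesis. And pairing each evening MADRS-S with the next morning's scan yields five pairs, leaves the Visit 3 scan without a partner, gives Visit 8 two candidate scores, and spans the change of recall version.

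The long-format data (9.4.8) would allow a later analysis. But one chosen after unblinding carries less weight than one written down now.

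**Conclusion.** The point holds as one of unused data and an untested hypothesis. Four of six FC-IMS-12 pairs enter neither secondary test, and no planned analysis relates the daily sgACC-DMN trajectory to mood, although the synopsis, 2.1 and section 3 pose that question.

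Two stronger conclusions are tempting and unsupported. The first is that the planned correlation is invalid; it matches its formal hypotheses. The second is that a six-visit model is simply more powerful and should replace it. At 40 per arm with sham r = 0, the within-person model loses about 3 to 13 points if coupling is only through person-level slopes. It gains substantially (27–28% to 76–85% at r = 0.30) if mood and FC vary together day to day. Six-visit slopes gain about 6 to 14 points with independent scan noise (3 if scans are nearly noise-free) and nothing with AR(1) 0.5 noise. Since the documents do not say which structure applies, the case rests on answering the stated question, not on power. It is an improvement that should be made.

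**What to change.** Keep the Fisher-z comparison as the formal secondary test. Before unblinding, add to 9.4.3 a supporting repeated-measures analysis over Visits 3 to 8:

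1. **IMS-12 leads**, paired with the same-morning scan. Regress mood on within-person-centred FC, arm, visit, arm × visit and FC × arm. Use participant-clustered robust SEs with a named small-sample correction, or random participant slopes for time; a participant intercept alone is not enough. Report the within-active FC slope with its 95% CI and the FC × arm contrast, and add a one-day-lag version.
2. **Linear hypothesis.** Also report the model with linear session number in place of visit terms, or correlate per-person six-visit slopes of FC and mood by arm.
3. **MADRS-S.** Pair each evening score with the next-morning scan, pair the Visit 3 scan with a pre-treatment score, state which score is used at Visit 8, and run a sensitivity analysis restricted to the 24-hour version.
4. **Status.** State that this analysis supports the formal test and does not replace it.

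The cost is SAP wording, one more model to specify and a little more analysis. It needs no new visits, scans or participants.
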